### Disclaimer and acknowledgment

This report has been carried out under grant agreement [No. 945218](#) from the European Union's Horizon 2020 research and innovation programme. The sole responsibility for the content of this report lies with the GERONTE consortium. It does not necessarily reflect the opinion of the European Union. The European Commission is not responsible for any use that may be made of the information contained therein.

## History of Changes

Version	Date	Author	Description of change
V1.0	2022-03-31	[name] [UBx]	First version
V2.0	2023-02-01	[name] [KUL]	Modifications following the expert opinion

## Executive Summary

### Deliverable work status

Deliverable	Completion status in %	Deviation	Data complete or to be updated
D4.1 Clinical trial methodology	100%	Deviation of content (see 'Attainment of the objectives and explanation of deviations')	Data complete
Associated Deliverables	D4.3 First study subject approvals package for FRONE D4.4 First study subject approvals package for TWOBE		
Associated Objectives	O4 Demonstrate in 16 study sites from three EU countries the feasibility and effectiveness of the GerOnTe model		

### Description of deliverable

This deliverable is a summary of the clinical trial methodology that will be included in the final version of the FRONE and TWOBE trial protocol.

This deliverable is connected to D4.3 First study subject approvals package for FRONE and D4.4 First study subject approvals package for TWOBE. This summary of the clinical trial methodology will be included in the final version of the FRONE and TWOBE trial protocol as part of the approvals packages.

The deliverable is associated to O4 Demonstrate in 16 study sites from three EU countries the feasibility and effectiveness of the GerOnTe model. D4.1 briefly describes the methodology of the FRONE and TWOBE clinical trials. Proof of concept will be done in these two clinical trials in three EU countries, namely France, Belgium and the Netherlands, using the clinical trial methodology described in D4.1.

### **Attainment of the objectives and explanation of deviations Attainment of the objectives**

The objectives related to this deliverable have been achieved in full, but modifications were made to the content of D4.1 as described in Annexe 1 (Description of the Action Part A) of the Grant Agreement N°945218. The deviations in D4.1 will be explained in the section below.

### **Explanation of deviations**

For D4.1, we stated in the Grant Agreement that the number of patients recruited per clinical trial would be 634 and per centre would be 79-80 patients during 18 months accrual in order to evaluate the impact of the GerOnTe intervention on Quality of Life at 1 year. It was initially planned that the study duration would be 1 year for all included patients, and that Quality of Life would be evaluated for each patient at 3, 6 and 12 months, taking the 12 months Quality of Life as primary endpoint, and 3 and 6 months Quality of Life as secondary endpoints.

During the development of the research protocol, the GerOnTe Trial Development Team (TDT) had intense discussions on the optimal timing of Quality of Life evaluation as primary endpoint. We decided to maintain the 1-year follow-up for all patients, and keep the 3, 6 and 12 months Quality of Life evaluation, but changed the primary endpoint from 12 months to 6 months.

The main reason for this change in primary endpoint was the concern about an excessive drop-out rate if all patients had to reach the 12 months' time point to complete the study. At KU Leuven (KUL), a recent, unpublished trial was performed with a geriatric intervention including a similar population. The primary endpoint for that trial was Quality of Life at 6 months.

First analyses (that became available in 2022) showed that dropout range was around 20% at 6 months in this population. These numbers were not available when the initial grant proposal was written in 2018. The GerOnTe Trial Steering Committee (TSC) decided to change the primary endpoint from 1 year to 6 months because there were concerns that the dropout rate would be too high at 12 months. It was also decided to increase the allowed dropout rate at 6 months from 10% to 20%.

The Trial Steering Committee (TSC) evaluated that it was not needed to put the expected dropout rate for GerOnTe higher than 20% since the GerOnTe population (breast, lung, colorectal, prostate cancer, including many patients treated with local therapy alone) has a better 'oncological prognosis' than the KU Leuven trial that included all tumor types, and only allowed patients starting systemic therapy. A new sample size calculation was performed based on these assumptions. Based on this calculation, the number of patients to be recruited was changed from 634 to 720 per clinical trial. Per clinical site, 90 patients will be recruited during the 18 months of inclusion. This change would only require a minor increase in accrual rate per site (10 patients per 2 months instead of 8 patients per 2 months), and this was assessed as easily feasible by all sites (given the broad inclusion criteria that were established). In addition, this change does not have any impact on the study accrual period or the 12 months follow-up per patient that was planned anyhow.

#### New timeline for tasks and deliverables for WP4:

Task:	Description	Leader	Participants	Start	End
4.1	Coordination of the clinical trials	UBX	UBX, KUL, DIAK, MYPL, BOC, DCU	1	56
4.2	Clinical trial compliance to ethical and regulatory requirements	UBX	UBX, KUL, DIAK	1	19
4.3	Enrolment of participants in the three participating countries (16 clinical sites)	UBX	UBX, KUL, DIAK	29	38

4.4	Clinical trial data collection and management	UBX	UBX, KUL	M28	56
4.5	Statistical analysis and final statistical report	UBX	UBX, KUL, DIAK, BOC, DCU	M28	60
MS5	Recruitment of at least 500 patients for the correct analysis of RCT outputs				M42

Deliverables	Description	Delivery date
D4.1	Clinical trial methodology	M12
D4.2	Trial committees' charters	M12
D4.3	First study subject approvals package for FRONE	M18, update M25
D4.4	First study subject approvals package for TWOBE	M18, update M26
D4.5	Mid-term recruitment report for FRONE	M36
D4.6	Mid-term recruitment report for TWOBE	M36
D4.7	Full-term recruitment report for FRONE	M46
D4.8	Full-term recruitment report for TWOBE	M46
D4.9	eCRF collection complete database	M56
D4.10	statistical analysis plan	M22, Update M26
D4.11	statistical analysis report	M60
D4.12	Status of posting results for FRONE	M60
D4.13	Status of posting results for TWOBE	M60

### Justification for delay in deliverable submission

The objectives related to this deliverable have been achieved on time and as scheduled in Annexe 1 (Description of the Action Part A) of the Grant Agreement N°945218.

## Glossary

ADL	Activities of Daily Living scale
APN	Advanced Practice Nurse
EORTC	European Organisation for Research and Treatment of Cancer
HAD	Hospital Anxiety and Depression scale
ITT	Intention To Treat
MTB	Multidisciplinary Tumor Board
PFS	Progressive Free Survival
SNDS	National Health Data System

## 1. Introduction

### 1.1. GERONTE and its objectives

GERONTE is a 5-year research and innovation project (April 2021 to Mars 2026) funded by the European Union within the framework of the H2020 Research and Innovation programme, in response to the health societal challenge topic SC1-BHC-24-2020 “Healthcare interventions for the management of the elderly multimorbid patient”. The overall aim of GERONTE is to improve quality of life - defined as well-being on three levels: global health status, physical functioning and social functioning- for older multimorbid patients, while reducing overall costs of care. To this end, GERONTE will co-design, test, and prepare for deployment an innovative cost-effective patient-centred holistic health management system, hereafter referred to as the GERONTE intervention. GERONTE intervention will rely on an ICT based application (Holis™) for real-time collection and integration of standardised clinical and home patient-reported data. GERONTE intervention will be demonstrated in the context of care of multimorbid patients having cancer as a dominant morbidity, and be adaptable to any other combination of morbidities.

#### Objectives

**O1: INFORMATION** gather the stakeholders and data needed for patient-centred and multi-actor complex decision-making process and management

**O2: TOOLS** develop ICT tools for the GERONTE intervention to be implemented

**O3: METHODS** develop socio-economic methods for evaluating the impacts of the implementation of the GERONTE intervention

**O4: DEMONSTRATION** demonstrate in 16 study sites from three EU countries the feasibility and effectiveness of the GERONTE intervention

**O5: REPLICATION** develop recommendations for the replication of GERONTE best practices in all European health systems

**O6: ENGAGEMENT** engage all stakeholders by co-designing the GERONTE intervention

### 1.2. Rationale

The current work corresponds to deliverable D4.1, which is part of work-package 4 which supports GERONTE objective 3 “Demonstration and validation”. The objective of WP4 is to perform two clinical trials, i.e. FRONE in France and TWOBE in Belgium and the Netherlands, in accordance with ethical and regulatory requirements. The goal is to provide a Proof of Concept of the GerOnTe model in three distinct European countries, and (i) to provide data on how the GerOnTe intervention fits into different health organisation systems, and (ii) to quantify the effectiveness and efficiency of GerOnTe system.

## 2. Study objectives

### 2.1. Primary objective

The primary objective of GerOnTe trials is to evaluate the effectiveness of the GerOnTe, ICT-based, integrated care pathway to improve patient 6-month quality of life, in France.

### 2.2. Secondary objectives

The secondary objectives of GerOnTe trials are, in the context of a French health-system organization for FRONE and in the Belgium and Dutch health-system context for TWOBE, to:

- Evaluate the effectiveness of the GerOnTe patient-centered system to:
  - Improve quality of life at 3, 9 and 12 months (secondary endpoint #1),
  - Improve patient survival and progression-free survival at 12 months (secondary endpoint #2),
  - Improve patient autonomy at 3, 6, 9 and 12 months (secondary endpoint #3),
  - Reduce patient anxiety at 3, 6, 9 and 12 months (secondary endpoint #4),
  - Reduce patient unplanned hospitalizations and patient institutionalizations at 6 and 12 months (secondary endpoint #5);
- Evaluate the efficiency of the GerOnTe patient-centered system through a cost-utility analysis. The medico-economic analysis will focus on the entire care pathway from the beginning of patient management with the GerOnTe system up to 1-year post-inclusion (3, 6, 9 and 12 months after inclusion) (secondary endpoint #6);
- Evaluate caregiver burden in health, psychological well-being, finances, social life and relationship with patient at 3, 6, 9 and 12 months after patient inclusion (secondary endpoint #7);
- Evaluate patient-reported overall experience of the GerOnTe system at 6 and 12 months' post-inclusion (secondary endpoint #8);
- Evaluate patient and health professionals reported overall satisfaction and acceptability of GerOnTe system at 6 and 12 months (secondary endpoint #9);
- Analyze the implementation and use of the GerOnTe patient-centred system by patients and professionals (secondary endpoint #10).
- Ancillary studies

## 3. Study endpoints

### 3.1. Primary endpoint

Quality of life assessed by the EORTC QLQ-C30 (version 3.0) questionnaire at 6 months after GerOnTe inclusion.

Three scales of the QLQ-C30 questionnaire are considered as primary endpoints:

- Normalised global health status score of the QLQ-C30 (version 3.0) questionnaire at 6 months after inclusion (score 0-100);
- Normalised score of the physical functioning scale of the QLQ-C30 (version 3.0) questionnaire at 6 months after inclusion (score 0-100);

Normalised score of the emotional functioning scale of the QLQ-C30 (version 3.0) questionnaire at 6 months after inclusion (score 0-100).

## 3.2. Secondary endpoints

### 1. Quality of life

- Normalised scores of global health status, physical functioning scale and emotional functioning scale of the QLQ-C30 (version 3.0) questionnaire collected at 3, 9 and 12 months after inclusion;
- Normalised Scores of the following QLQ-C30 scales/items assessed at 3, 6, 9 and 12 months after inclusion: role functioning scale, cognitive functioning scale, social functioning scale, fatigue scale, nausea scale, pain scale, dyspnea item, insomnia item, appetite loss item, constipation item, diarrhea item and financial difficulties item.
- Scores of the following QLQ-ELD14 scales/items assessed at 3, 6, 9 and 12 months after inclusion: assess mobility scale, worries about others scale, future worries scale, maintaining purpose scale, burden of illness scale, joint stiffness item, family support item. The QLQ-LD14 questionnaire is a complementary module to the QLQ-C30 and taking into account the specific needs of elderly patients.

### 2. Survival

- Overall survival at 12 months after inclusion;
- Progression-free survival (PFS) defined as the time from study treatment initiation to the first occurrence of disease progression or death (of any cause), whichever occurs first.

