#### 4.2. Duration of study (whole population)

The total duration of the study will be approximately 30 months, including 18 months of active enrollment.

Planned start date (first participant on study): September 2022.

The planned study termination (clinical cutoff) corresponds to the date when each participant has been followed-up for 12 months or is deceased.

End of study occurs when all of the following criteria have been satisfied:

- The trial is closed to enrollment

AND

- The last included participant has been followed for 12 months or if deceased, each participant has been followed-up for 12 months or is deceased.

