### 4.3. Definitions of duration of study per participant

Depending on the period (light or dark blue on the figure 2), participants will be included either in the control arm or in the intervention arm.

Participants will be evaluated at scheduled visits as described in section 7.

Each participant will be followed-up for 12 months after inclusion.

If funding permits, a follow-up of patients up to five years after protocol inclusion will be planned. Minimal data will be collected from patient's chart including relapse or progression, survival and institutionalisation.

Participants will be considered to be **on-study** from the signature of the informed consent to the end of follow-up period.

Participants may withdraw their consent at any time; no further study activities will be conducted with them.

**Study discontinuation** occurs when an enrolled participant ceases to participate in the study, regardless of the reason (as detailed under “Follow-up” in Section 7). Participants have the right to withdraw consent at any time; if this is the case, no further follow-up should be performed.

The date and reason for study discontinuation will be clearly documented in the participant’s eCRF.

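### PFS is timed from an undefined start of study treatment, while overall survival and the 12-month follow-up run from inclusion

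*Protocol*

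**What the plan says.** Section 3.2, item 2 of the protocol lists two survival endpoints, one under the other, with different starting points:

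- Overall survival: "Overall survival at 12 months after inclusion".
- PFS: "Progression-free survival (PFS) defined as the time from study treatment initiation to the first occurrence of disease progression or death", death being from any cause.

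The term study treatment is not explained and is not used again in the document.

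The matching objective in section 2.2 is "Improve patient survival and progression-free survival at 12 months (secondary endpoint #2". It gives a time point but no origin.

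Follow-up is counted from inclusion. Section 4.3 says "Each participant will be followed-up for 12 months after inclusion", and section 4.2 says "The planned study termination (clinical cutoff) corresponds to the date when each participant has been followed-up for 12 months or is deceased". Section 4.3 has patients on study "from the signature of the informed consent to the end of follow-up period".

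The intervention under test is not a cancer treatment. Section 2.1 sets out to "evaluate the effectiveness of the GerOnTe, ICT-based, integrated care pathway". The cancer treatments themselves are mixed: the explanation of deviations in the Executive Summary describes the population as "including many patients treated with local therapy alone".

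**The concern.** A comparison of time to event between arms needs an origin that every patient has, that means the same in both arms, and that the intervention cannot move. Inclusion meets these conditions. The stated PFS origin does not clearly meet any of them, because the protocol does not say which event it is.

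Two readings are possible, and they are alternatives. The treatment may be the GerOnTe pathway, or it may be the patient's cancer treatment. The first leaves the control arm without a clock. The second leaves out patients who never start treatment and uses a date that the pathway might influence. At stake is whether PFS can be compared between arms on the same patients and the same clock as overall survival, and whether the 12-month time point lies within planned follow-up.

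**Working it through.** The protocol states no PFS rate, event count or power, so there is no figure of its own to reproduce. The check sets the passages side by side and then does the follow-up arithmetic.

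**Reading 1: study treatment is the GerOnTe pathway.** Under sections 4.1 and 4.3, patients included before their site switches are controls and do not receive the pathway. They have no start date for it, so PFS is undefined for the planned 360 control patients per trial (table in section 5.1), and no comparison is possible.

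**Reading 2: study treatment is the cancer treatment.**

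- Patients who never start treatment have no PFS time. Section 5.1 defines an intention-to-treat population that keeps every patient, so the endpoint and the population do not fit together.
- Section 3.2, item 10 counts, as a measure of use, tumour-board and other treatment-decision meetings that work from the complete dashboards. This makes it plausible that the pathway affects whether or when treatment starts. If so, the origin and the analysed set could differ by arm. The protocol does not state such an effect.

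**Timing under reading 2.** Let d be the months from inclusion to treatment start. The protocol gives neither its sign nor its size. Follow-up ends 12 months after inclusion, so follow-up from the PFS origin is 12 − d.

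- d = 0: 12 months, no gap.
- d > 0: the shortfall equals d, and events between inclusion and treatment start have no PFS time. With d = 3, for example, 12 − 3 = 9 months remain.
- d < 0: the 12-month point falls inside follow-up, but patients enter observation after their clock has started. This delayed entry would need to be handled.

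**Illustration for d > 0.** All of the following is assumed: exponential PFS from inclusion, the same d for all 720 patients of one trial, and 12-month PFS S between 90% and 60%.

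- Events before the origin = 720 × (1 − S^(d/12)).
- Difference between survival at 12 − d months and at 12 months = S^((12 − d)/12) − S.

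| d (months) | Follow-up from origin (months) | Events before origin, S = 90% to 60% | Survival difference (percentage points), S = 90% to 60% |
|---|---|---|---|
| 0.5 | 11.5 | 3.2 to 15.2 | 0.40 to 1.29 |
| 1 | 11 | 6.3 to 30.0 | 0.79 to 2.61 |
| 2 | 10 | 12.5 to 58.8 | 1.59 to 5.33 |

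Worked example for d = 1 and S = 0.60: 0.60^(1/12) = 0.9583, and 720 × 0.0417 = 30.0.

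**With PFS timed from inclusion.** d no longer enters. Every included patient has an origin, no event falls before it, and 12 months from the origin is the end of planned follow-up.

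**The case against.** The best defence is that this is a loose phrase in a summary document. The deliverable says that it will be built into the final trial protocol, it refers to a section 7 and an appendix that are not part of it, and it leaves detailed analysis to a separate plan. Censoring rules and the handling of untreated patients commonly belong there. That stands, and their absence is not held against the protocol. It does not remove the point, because the protocol does not leave the origin open: it states one, and an analysis plan that followed it would inherit the problem.

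Several stronger readings are tempting, and the document does not support them.

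- A reader might infer that 12-month PFS is unobservable or that the objective cannot be met. PFS is a time-to-event endpoint and can be analysed with censoring. Any shortfall is only the delay. The 12 months in section 2.2 can be read as running from inclusion, which follow-up covers. Section 4.3 also foresees follow-up to five years with progression and survival recorded, though only subject to funding.
- A reader might take it as given that treatment starts after inclusion, or that its start differs by arm. The protocol states neither.
- A reader might say that every other endpoint runs from inclusion. Section 3.2 gives no time point for the chair stand test or the frailty scale, and no origin for the cost-utility ratio. The contrast that holds is with overall survival and follow-up.
- The patient counts in the table are not evidence of size. They follow from assumed delays and assumed PFS.

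**Conclusion.** The point holds: the stated PFS origin is undefined and inconsistent with overall survival and with follow-up. Under the pathway reading, controls have no origin. Under the cancer-treatment reading, untreated patients have no PFS time, and the clock could depend on the arm. This follows from the text and needs no assumption.

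The consequences for early events and for the length of follow-up are conditional on when treatment starts, which the protocol does not say. A later start leaves earlier events without a place and shortens follow-up by the delay; an earlier start brings delayed entry. Under the assumptions shown, delays of 0.5 to 2 months would put about 3 to 59 of 720 patients' events before the origin. With no delay the number is zero.

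The weight is limited. PFS is one part of secondary endpoint 2. The primary analysis and the sample size rest on the QLQ-C30 scores and are unaffected.

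**What to change.** In section 3.2, item 2, define PFS as the time from inclusion to the first disease progression or death from any cause, in all included patients of both arms, with the same origin as overall survival. In section 2.2, add that the 12 months run from inclusion, so that the time point lies within planned follow-up. Carry the same definition into the analysis plan.

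The change to the endpoint is one line and alters neither the design nor the sample size. One item should be confirmed: the open-ended list of outcomes in section 4.1 names mortality but not progression, so the sponsor should check that progression dates are collected from inclusion in both arms. The document at hand does not show whether this needs any addition to data collection.

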### 3. Patient autonomy

- Dependence score of the Activities of Daily Living scale (ADL) assessed at 3, 6, 9 and 12 months after inclusion;
- Proportion of patients living at home 6 and 12 months after inclusion.
- Number of completed chair stands in 30 seconds (Chair stand test: participants stand up repeatedly from a chair for 30 seconds).
- Clinical frailty scale

